Typical clinical MR scanning requires the imaging of multiple contrasts (T1, T2, FLAIR) to provide radiologists with sufficient data for reporting purposes. However, these contrast images typically have no quantitative value and are defined by strict acquisition parameters that are not easily adjusted. Developmental changes or pathologies which affect tissue relaxation parameters often require non-standard parameters for optimal imaging. For example, T1 relaxation times in grey matter (GM) and white matter (WM) at 1.5T will range from 2000 and 3000ms, in very preterm born neonates at birth, but will decrease to 1100 and 800ms by adulthood. The two- to three-fold decrease in relaxation times, coupled with GM-T1 becoming longer than WM-T1 with age, necessitates dramatically different imaging parameters. These changes in T1 with age, and similarly with T2, vary by subject and are very difficult to determine *a priori*. Consequently, current practise is to set general parameters by approximate age group – Neonates (<1 mth), Infants (1mth-2yr), Adolescents (2yr-12yr), and Teenagers/Adults (13+). However, as both T1, and T2 continue to change with age, and may be affected by pathology, i) **image contrast using generic parameters is often sub-optimal** and ii) **total exam times may be increased** in an attempt to improve contrast by adjusting parameters on the fly.

An alternative approach to imaging specific contrasts is to directly quantify tissue parameters – T1, T2, Proton Density (PD) – and use these quantitative parameters to generate the desired contrast images after acquisition. In doing so, i) **scan times may be reduced** as there will be no need to ‘guess’ or adjust acquisition parameters, and ii) almost **any image contrast may be generated**. Clinical adoption of quantified imaging has been hampered by the lack of an elegant pulse sequence and appropriate software that is compatible with typical clinical workflow.

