Synthetic MR Technologies is attempting to address this issue by providing the **software** and the **pulse sequence** (in partnership with the major MR manufacturers) to bring MR quantification into clinical usage. The MDME sequence aims to provide whole absolute quantification of T1, T2, PD and B1 inhomogeneity in **5 minutes** at typical clinical resolution (0.8 x 0.8 x 5mm). SyMRI software then allows a user to synthesize any almost image contrast (T1, T2, PD, FLAIR, IR, DIR, etc) by adjusting imaging parameters after the fact. Conventional T1, T2, and FLAIR acquisitions would take a minimum of 12 minutes, and may need to be repeated if image contrast is poor. Not only could **total exam times be reduced**, by taking image generation offline, but **scan quality can be improved**, by enabling the examination of various contrast images that otherwise would not have been obtained.

There is great potential for this solution at the Hospital for Sick Children. A significant portion of the brain imaging performed at Sickkids involves neonates and infants, which pose a unique problem in that tissue contrast changes rapidly during this period (ideal sequence at 3 months, is less useful at 6 months). Consequently, image contrast and therefore quality is often sub-optimal. Furthermore, a combined T1, T2 and FLAIR sequence would **save at least 5 minutes** per subject. Time savings could be even greater as the need for repeat scanning due to poor contrast could be eliminated.

To explore this opportunity, Sickkids and SyMRI would like to sign an evaluation agreement in partnership with Philips and Siemens to trial the MDME sequence and SyMRI software. Philips would provide the pulse sequence. SyMRI would provide the software and technical support. Sickkids would test the sequence initially in small population of adults (6-10) and then acquire a large cohort of neonates, infants, adolescent, and teenagers.

From a regulatory perspective, SyMRI is considered a Class II medical device. To proceed with this proposal, Sickkids will be filling an application for Investigational Testing Authorization (ITA) with Health

Canada on behalf of Synthetic MR. This application requires REB approval, and as an unfunded study, the REB application requires scientific Peer Review.

Select Publications

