Clinical Utility – SyMRI's average rating as 'Better', 'Equal', or 'Worse' than conventional imaging will be tabulated from all reviewer responses. Assigning a value of 3, 2, and 1 respectively to these ratings – SyMRI is expected to average no lower than a 2.0 – at least equal to conventional imaging. Paired parametric (t-test) and non-parametric (wilcoxon signed-rank) statistical tests will be used to compare time spent using SyMRI vs Conventional MRI to determine if one approach is significantly faster than the other.

Quantitative Image Quality – Image SNR in WM/GM will be calculated and compared between conventional MRI and SyMRI (used to generate fixed / comparable contrasts). Paired parametric (t-test) and non-parametric (wilcoxon signed-rank) statistical tests will be used to evaluate if one approach is significantly better than the other.

Scan Time Reduction – Average scan time of SyMRI vs. Conventional MRI will be computed based on timing data stored in the MR images. A minimum of 5 minutes of scan time is expected to be saved using SyMRI.

6. Budget

No funding is required for this study. Software and installation will be provided by SyMRI and Philips at no charge. Work completed by WL will fall under his existing responsibilities.

7. Project Overview

- 1) Evaluate product performance relative to conventional T1, T2, FLAIR, qT1 and qT2
 - a) Preliminary evaluation – 6 adult volunteers (>18 years of age)
 - b) Clinical Evaluation
 - i) **25 neonates (<1 month of age)**
 - ii) **25 infants (1mth – 2 years of age)**
 - iii) **25 adolescents (2 – 12 years of age)**
 - iv) **25 teenagers (13-18 years of age)**
- 2) Evaluation
 - a) Scan Time Impact - Scan report forms, documenting time spent scanning SyMRI, vs conventional MRI.
 - b) Quantitative – Comparison of conventional and synthetic MR images using Matlab.
 - i) SNR, CNR. Repeatability of images.
 - c) Qualitative – Train radiologists / fellows to use SyMRI software. Complete questionnaire with respect to experience working with software. Diagnostic quality of SyMRI image
- 3) Data to be provided by Sickkids to SyMRI
 - a) 4 in-vivo clinical imaging datasets including conventional clinical and product protocol
 - i) De-identified DICOM images including clinical interpretation and commentary
 - ii) 2 neonatal/infant and 2 adolescent/teenager

8. Estimated Timelines / Milestones

- 1) Sequence delivery (Philips, SyMRI, Sickkids) – Q4, 2015

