- 2) Software delivery / installation (SyMRI, Sickkids) – Q4, 2015
- 3) Adult acquisition and evaluation complete (Sickkids) – Q4, 2015
- 4) Clinical evaluation (Sickkids) – 5 neonates + 5 adolescents / month – Ongoing
- 5) Initial data sharing and commentary (SyMRI, Sickkids) – Q4, 2015
 - a. 1 from neonatal/infant and 1 from adolescent/teenager provided to SyMRI
- 6) Clinical acquisition complete (SyMRI, Sickkids) – Q1, 2016
 - a. 1 from neonatal/infant and 1 from adolescent/teenager provided to SyMRI
- 7) Product evaluations complete and provided to SyMRI (SyMRI, Sickkids) – Q1, 2016
- 8) Sequence delivery (Siemens, SyMRI, Sickkids) – Q1, 2017
- 9) Research Acquisition (SyMRI, Sickkids) – 2017
- 10) Clinical Acquisition (Philips, Sickkids) – 2017
- 11) Product evaluation (Sickkids, SyMRI, Siemens, Philips) – Q4 2017

9. Recruitment Considerations

Inclusion / Exclusion criteria

Any stable patient undergoing clinical MRI of the brain is eligible for this study. Only those patients where an additional 10 minutes of MR imaging would not be advisable (ie. unstable, implants) will be excluded.

Research patients undergoing research MRI of the brain for another study will be eligible. Only those subjects where an additional 10 minutes of MR imaging cannot be accommodated into their original booking will be excluded.

Risks and benefits to patients

There are no risks associated with SyMRI. The pulse sequence is a modified clinical imaging sequence and does not approach any scanner safety limits. For Philips, the sequence has been approved by the scanner manufacturers themselves and will be installed by their employees. For Siemens, the sequence will be obtained as part of a C2P agreement between Karolinska University Hospital and The Hospital for Sick Children. There is no possibility of adverse events beyond those associated with normal clinical MR imaging.

Patients involved in the validation of SyMRI may benefit from the improved diagnostic capabilities of SyMRI (custom image contrasts). This may eliminate the need for a repeat MRI session as required images may be generated through post-processing. Future patients would also benefit from reduced scan times.

Consent and data sharing

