SyMRI Statistical Analysis Plan

Reducing scan times and improving care through quantitative imaging:

Evaluating SyMRI in pediatric populations

[name], [name], [name]

Analysis

SyMRI will be primarily evaluated on its ability to generate clinically useful images, and if it can be used to reduce total scan times in all, or some, of the target age groups. A secondary output of this project will be to evaluate the usability of SyMRI software and determine if it could be reasonably integrated into a radiologist's existing workflow.

Clinical Utility – SyMRI's average rating as 'Better', 'Equal', or 'Worse' than conventional imaging will be tabulated from all reviewer responses. Assigning a value of 3, 2, and 1 respectively to these ratings – SyMRI is expected to average no lower than a 2.0 – at least equal to conventional imaging. Paired parametric (t-test) and non-parametric (wilcoxon signed-rank) statistical tests will be used to compare time spent using SyMRI vs Conventional MRI to determine if one approach is significantly faster than the other.

Quantitative Image Quality – Image SNR in WM/GM will be calculated and compared between conventional MRI and SyMRI (used to generate fixed / comparable contrasts). Paired parametric (t-test) and non-parametric (wilcoxon signed-rank) statistical tests will be used to evaluate if one approach is significantly better than the other.

Scan Time Reduction – Average scan time of SyMRI vs. Conventional MRI will be computed based on timing data stored in the MR images. A minimum of 5 minutes of scan time is expected be saved using SyMRI.

Evaluation:

- 1) Evaluate product performance relative to conventional T1, T2, FLAIR, qT1 and qT2
 - a) Preliminary evaluation – 6 adult volunteers (>18 years of age)
 - b) Clinical Evaluation
 - i) **25 neonates (<1 month of age)**
 - ii) **25 infants (1mth – 2 years of age)**
 - iii) **25 adolescents (2 – 12 years of age)**
 - iv) **25 teenagers (13-18 years of age)**
- 2) Evaluation
 - a) Scan Time Impact - Scan report forms, documenting time spent scanning SyMRI, vs conventional MRI.
 - b) Quantitative – Comparison of conventional and synthetic MR images using Matlab.
 - i) SNR, CNR. Repeatability of images.

- c) Qualitative – Train radiologists / fellows to use SyMRI software. Complete questionnaire with respect to experience working with software. Diagnostic quality of SyMRI image
- 3) Data to be provided by Sickkids to SyMRI

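### The SNR comparison controls contrast but not voxel size, so if resolutions differ, a significant result in either direction cannot be read as a difference in image quality

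*SAP*

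**What the plan says.** The SAP (Analysis, Quantitative Image Quality) states: "Image SNR in WM/GM will be calculated and compared between conventional MRI and SyMRI (used to generate fixed / comparable contrasts". The protocol's section 5 has the same paragraph. Both plan a paired t-test and a Wilcoxon signed-rank test, and in the protocol's words these "statistical tests will be used to evaluate if one approach is significantly better than the other". The SAP's Evaluation list adds CNR and repeatability under "Comparison of conventional and synthetic MR images using Matlab". Neither document mentions voxel size, resampling or normalisation in the analysis.

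The only resolution figure is in the protocol's Background, which says that the sequence aims to quantify tissue parameters "at typical clinical resolution (0.8 x 0.8 x 5mm"). No voxel size is given for any conventional sequence.

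The study does not define the conventional scan:

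- Section 4 adds the SyMRI sequence to the clinical examination already scheduled.
- The Background says of conventional imaging that "current practise is to set general parameters by approximate age group", and that parameters may also be adjusted during the examination.
- Section 9 adds: "Research patients undergoing research MRI of the brain for another study will be eligible".
- The revision overview extends recruitment to research and CDIU scanners, and section 8 adds a Siemens sequence to the Philips one.

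**The concern.** Raw SNR depends on voxel size as well as on how good the imaging method is. A larger voxel collects more signal and gives higher SNR at the price of resolution. Making contrast comparable does not deal with this. Nor does pairing: it removes differences between children, whereas a voxel mismatch is a difference between the two methods within each child.

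If the two acquisitions differ in resolution, the planned tests can therefore declare one approach better when only voxel volume differs. SNR and CNR are the named quantitative half of the image-quality question in section 2, which is meant to inform a purchase decision and support for Health Canada approval. An SNR result that cannot be attributed to image quality weakens that half of the answer.

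**Working it through.** The documents give no alpha, SD, expected difference or power for this endpoint, so there is no figure of the plan's own to reproduce. The check has two steps.

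**Inputs from the documents.** The SyMRI voxel is 0.8 x 0.8 x 5 mm, stated as an aim (protocol, Background). There are 25 children in each of four age groups, 100 in all (SAP, Evaluation).

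**Assumptions.** The conventional voxel sizes are assumed. SNR is taken as proportional to voxel volume, other parameters equal. The test is a two-sided paired t-test on log SNR at alpha 0.05, with an SD of the within-pair log ratio from 0.1 to 0.5.

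**Step 1: SNR ratio from volume alone.** The SyMRI voxel volume is 0.8 x 0.8 x 5 = 3.2 mm³. The ratio is r = 3.2 / (conventional voxel volume).

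| Assumed conventional voxel | Volume (mm³) | r | Favours |
|---|---|---|---|
| 0.8 x 0.8 x 5 mm | 3.20 | 1.00 | neither |
| 0.8 x 0.8 x 4 mm | 2.56 | 1.25 | SyMRI |
| 0.8 x 0.8 x 3 mm | 1.92 | 1.67 | SyMRI |
| 1 mm isotropic | 1.00 | 3.20 | SyMRI |
| 0.9 x 0.9 x 5 mm | 4.05 | 0.79 | conventional |

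**Step 2: chance of a significant result with no quality difference.** If all pairs share the same r, the t statistic is noncentral with n − 1 degrees of freedom and noncentrality |ln r| × √n / SD. For r = 1.25, n = 25 and SD 0.5, this is 0.223 × 5 / 0.5 = 2.23, and the test rejects about 57% of the time.

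| r | n | SD 0.5 | SD 0.3 |
|---|---|---|---|
| 1.00 | 25 or 100 | 5% | 5% |
| 1.25 | 25 | 57% | 95% |
| 0.79 | 25 | 62% | 96% |
| 1.25 | 100 | 99% | about 100% |
| 0.79 | 100 | about 100% | about 100% |

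The volume ratio that gives 80% rejection is:

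| n | SD 0.1 | SD 0.2 | SD 0.3 | SD 0.5 |
|---|---|---|---|---|
| 25 | 1.06 | 1.12 | 1.19 | 1.34 |
| 100 | 1.03 | 1.06 | 1.09 | 1.15 |

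Under these assumptions, a modest and consistent mismatch is enough to decide the test, even within a single age group.

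**The case against.** **The documents point towards similar resolution.** The Background describes SyMRI's resolution as typical of clinical practice, and no conventional voxel size contradicts that. A reader might infer that SyMRI's voxels are fixed and that the conventional ones are different. Neither is supported. In the SAP the word fixed describes the contrasts, and the SyMRI dimensions are an aim. This part of the objection stands: matching is unspecified, and a mismatch is not shown. But a Background description is not an analysis rule, and it does not speak for other studies' research protocols.

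**The research route is partly inference.** Section 9 makes research patients eligible, but it does not say that their research sequences serve as the conventional comparator, and it does not say how many there will be. This stands. It means that the share of pairs affected is unknown, and that the 1 mm isotropic case is only an illustration.

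**Volume normalisation does not isolate image quality.** The sequences differ in type and duration. SyMRI aims at 5 minutes, while "Conventional T1, T2, and FLAIR acquisitions would take a minimum of 12 minutes". If those 12 minutes are assumed to split equally at 4 minutes per contrast, and SNR to scale with the square root of scan time, time alone gives √(5/4) = 1.12. That falls within the range of ratios in the working that give 80% rejection. This also stands. It is a reason to keep raw SNR, which describes the images as delivered, and not to make normalised SNR the sole basis of the test.

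**SNR is one measure among several.** It has no success threshold, and the radiologists' ratings may register a loss of resolution that SNR misses. This limits how far the problem reaches. It does not remove it from the SNR result.

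**Conclusion.** The gap is real. The plan tests raw WM/GM SNR with contrast made comparable, and it has no rule that would detect or handle unequal voxel sizes. Followed exactly, it could credit a voxel-size difference to image quality.

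The size depends on conventional resolutions that the documents do not give. The volume-driven ratio is 1.0 if voxels match and ranges from 0.79 to 3.2 across the assumed sizes. At 25 pairs, an assumed 4 mm conventional slice (ratio 1.25) would by itself give a significant result in about 57% of trials at SD 0.5 and 95% at SD 0.3. These percentages also assume alpha 0.05, strict proportionality of SNR to volume, and the same mismatch in every pair.

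A reader might conclude that the comparison is biased in SyMRI's favour. The documents do not support that. The direction depends on which voxel is larger, and larger conventional voxels would penalise SyMRI. Nor do the documents give any basis for saying that most pairs are affected. The point concerns how one quantitative measure is interpreted and does not undermine the evaluation as a whole.

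**What to change.** In the SAP, before the SNR results are seen:

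1. Extract the acquired voxel dimensions (in-plane size and slice thickness) from the image headers for every pair and contrast, and report them for both methods.
2. Keep the raw SNR and CNR comparison, in the same WM and GM regions for both methods.
3. Add (a) the same paired tests restricted to pairs whose voxel volumes agree within a stated tolerance, such as 10%.
4. Add (b) the paired tests on SNR and CNR divided by voxel volume.
5. Claim significantly better image quality only if the result holds in (a) or (b), and note that differences in scan time and sequence type remain.

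The tolerance in (a) is a compromise. A consistent residual mismatch near 10% could still matter if the within-pair SD is small, since a ratio of 1.06 gives 80% rejection at n = 25 and SD 0.1. Reporting (b) beside (a) shows whether that is happening.

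The cost is SAP wording and a few lines of the Matlab analysis. No extra scanning is needed, and the plan already draws timing data from the stored images. The downsides are fewer pairs in (a) and an SNR difference that may shrink, whichever method it favours.

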Exhibit C – SyMRI and Sickkids Project Plan

Reducing scan times and improving care through quantitative imaging:

Evaluating SyMRI in pediatric populations

[name], [name] [name]

Revision overview

New Time Frame – Until end of 2017 for additional recruitment

Expanded to include participants on Research MRI and CDIU MRI

Increase # of patients

+25 Neonatal

+75 All ages

Added [name] as co-PI

1. Lay Summary

Typical magnetic resonance imaging (MRI) involves taking many images called 'contrasts' to look at the body in different ways. Standard scan settings are usually good enough for a radiologist to review. The best settings often change with the age of the patient and their health, and are time consuming to determine. Quantified imaging is an alternative to contrast-based imaging which explicitly measures tissue properties and can be used to create almost any contrast. This method of imaging has been held back by a lack of the right software. Synthetic MR Technologies has created a quantified imaging solution - **SyMRI** - to enable radiologists to acquire quantified images and always obtain the best contrast images.

2. Objective

The objective of this study is to evaluate SyMRI in a pediatric population to determine if Sickkids would be interested in purchasing this product / support Health Canada approval. Specifically, we are interested in determining if SyMRI is clinically useful:

- Is synthetic imaging quality comparable / better than conventional imaging?
 - o Qualitative – Are radiologists more confident using synthetic MR vs conventional
 - o Quantitative – Signal-to-noise (SNR) and Contrast-to-noise (CNR)
- To what extent can total exam times be reduced?
- Is the software user friendly and would our radiologists use it?

SyMRI will be integrated in future MR systems manufactured by GE and Philips. For GE, their next MR system software releases (DB25 and Signa Pioneer) will include SyMRI as a purchasable option – FDA approval is expected in Q2 2015. Philips is targeting Q2/Q3 2015 for releasing SyMRI on its 1.5T and 3T platforms. To evaluate this product without regulatory approval (considered a Class II medical device) an Investigational Testing Authorization (ITA) must be filed with Health Canada. Local REB approval is required as part of the ITA application.

3. Background

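### The plan can show that SNR under SyMRI is better or worse but never that it is comparable, and CNR is listed for comparison without a statistical method or criterion

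*SAP*

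**What the plan says.** Protocol section 2 (Objective) asks "Is synthetic imaging quality comparable / better than conventional imaging". Beneath that question it lists a qualitative item, radiologists' confidence, and a quantitative item, SNR and CNR.

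The quantitative analysis is worded alike in Protocol section 5 and in the SAP under Quantitative Image Quality. It covers SNR only: "Image SNR in WM/GM will be calculated and compared between conventional MRI and SyMRI". A paired t-test and a Wilcoxon signed-rank test "will be used to evaluate if one approach is significantly better than the other". Neither document gives a significance level, a comparability limit or a confidence-interval rule for SNR.

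CNR appears again in item 2b of the SAP's Evaluation list (and of Protocol section 7), under a comparison of images in Matlab: "SNR, CNR. Repeatability of images".

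The SAP places these measures in a supporting role. It states that "SyMRI will be primarily evaluated on its ability to generate clinically useful images" and on whether scan time can be reduced. Both of those have a benchmark: "SyMRI is expected to average no lower than a 2.0" for the reader rating, and "A minimum of 5 minutes of scan time is expected be saved using SyMRI".

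**The concern.** The question is whether quality is comparable or better; the test asks whether there is a difference. A significant result in SyMRI's favour answers better, and one against it answers worse. No result is defined that answers comparable. A non-significant result may mean that SNR is similar, or that the data were too variable to show a real loss, and the test does not separate the two.

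For CNR the gap is different. The comparison is planned, but the plan does not say how CNR is computed, how it is summarised or what would count as a satisfactory result. Protocol section 3 argues that generic settings give sub-optimal contrast in children, so CNR is the quantitative measure closest to the product's claimed advantage.

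Protocol section 2 says the study is to inform a purchase decision and support Health Canada approval. A statement that SNR or CNR is comparable would carry weight in that setting, and the plan gives no basis for making it.

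**Working it through.** **No figure to reproduce.** The documents contain no power, sample-size or precision calculation for SNR or CNR. The mismatch is established by the text; the arithmetic below only shows what it could mean in practice.

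**Objective and analysis side by side**

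| | Objective | Analysis |
|---|---|---|
| SNR | comparable or better | tested for a difference only |
| CNR | comparable or better | listed for comparison; no method or criterion |

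**Inputs**
- From the documents: 25 children in each of four age groups, 4 × 25 = 100 (SAP, Evaluation 1b).
- Assumed: SD of the within-child log SNR ratio (SyMRI/conventional) of 0.2, 0.3 or 0.4; a common ratio and SD across ages; two-sided 5% level; a true 10% loss (ratio 0.90); an illustrative limit of 0.90, which is not a proposal.
- Also assumed: 75 children with a given conventional contrast. Protocol section 9 accepts any clinical or research brain MRI, and the documents do not say how many children will have each contrast.

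**Step 1: how often a 10% loss is non-significant.** With log(0.90) = −0.105, the noncentrality is 0.105 × √n / SD. At n = 100 this is 5.27, 3.51 or 2.63, against a critical t of 1.984. The probability that |t| stays below the critical value, from the noncentral t distribution, is:

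| n | SD 0.2 | SD 0.3 | SD 0.4 |
|---|---|---|---|
| 100 | 0.0006 | 0.0645 | 0.258 |
| 75 | 0.0055 | 0.149 | 0.385 |
| 25 | 0.285 | 0.608 | 0.756 |

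The n = 25 row applies only if SNR is tested within an age group, which the SAP does not specify.

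**Step 2: how often a limit of 0.90 would be met.** The rule is that the lower 95% confidence limit of the ratio exceeds 0.90. The noncentrality is log(true ratio / 0.90) × √n / SD.

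| True ratio, n | SD 0.2 | SD 0.3 | SD 0.4 |
|---|---|---|---|
| 1.00, n = 100 | 0.999 | 0.936 | 0.742 |
| 1.00, n = 75 | 0.995 | 0.851 | 0.615 |
| 0.95, n = 100 | 0.76 | 0.43 | 0.27 |

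For the last row, log(0.95/0.90) = 0.054, giving noncentralities of 2.70, 1.80 and 1.35.

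The first two rows are almost exactly one minus the matching rows of Step 1, because the distance from 1 to 0.90 is the same in both. They are the same calculation seen from the other side, not separate support.

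**Step 3: several comparisons.** Three contrasts (T1, T2, FLAIR) in two tissues give six SNR comparisons. If all six had to exceed 0.90 with truly equal SNR at n = 100, simulation with an assumed correlation of 0.5 gives 0.997, 0.770 and 0.386.

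No CNR figures are computed, because the documents give no CNR values.

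**The case against.** - **The 2.0 benchmark already covers comparability.** It does so for the reader rating, which belongs to the primary evaluation. It does not cover SNR or CNR, which the objective lists as a separate item. This objection limits the importance of the point but does not remove it.
- **A reader might infer that CNR is left out of the plan.** The documents do not support that. CNR is listed for a Matlab comparison; what it lacks is a formula, a statistical method and a criterion.
- **A reader might infer that the plan will report a non-significant SNR result as comparable.** Neither document says so. The plan leaves that reading open and supplies no alternative to it.
- **With 100 children a 10% loss is rarely missed.** That stands if the SD is 0.2 or 0.3 (0.1% or 6%). It weakens at 0.4 (26%) or with fewer usable pairs. The largest figures, 61% and 76%, need testing by age group. Even with high power, a difference test contains no definition of comparable.
- **This is an unfunded product evaluation.** That is fair, and it argues for a light remedy. It does not make the test answer the stated question.

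**Conclusion.** The point holds as a mismatch between objective and analysis on a supporting measure. As written, the SNR analysis can support better or worse but not comparable, and CNR has no stated basis for either conclusion. This follows from the text and needs no assumption.

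The practical size is uncertain. Under the assumptions shown, the chance that a 10% SNR loss is non-significant in 100 children runs from 0.1% to 26%, depending on an SD that the documents do not give.

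A reader might go further and conclude that the study's main evaluation is undermined. The documents do not support that: the primary evaluation rests on clinically useful images and scan time, each with its own benchmark. The point is worth correcting before analysis, with confidence in the wording problem and only moderate confidence in its numerical importance.

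**What to change.** Replace the rule based on a significant difference with estimation, in both the SAP and Protocol section 5.

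1. For each conventional contrast a child has, report the paired SyMRI/conventional SNR ratio in grey matter and in white matter, analysed on the log scale.
2. State the CNR formula and report the paired difference in absolute grey–white CNR. A difference is safer than a ratio because Protocol section 3 says the order of grey- and white-matter T1 changes with age, so T1-weighted CNR can be near zero.
3. Give each estimate a 95% confidence interval from the paired t analysis, with Wilcoxon as a sensitivity check. Show results overall and by age group, with the number of children contributing.
4. Before analysis, the investigators state a comparability limit for SNR and one for CNR, and the contrast or contrasts to which each applies.
5. Conclude comparable only if the lower confidence limit lies above the stated limit, and better only if it lies above 1 (ratio) or 0 (difference). Where no limit is set, report the estimate and interval only. Never infer comparability from non-significance.

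The change is to wording. CNR is already listed and can use the same tissue regions, so no new scans or readers are needed.

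The cost is that the investigators must commit to limits, and a strict one may be missed. With 100 children, the illustrative 0.90 limit on one comparison is met in over 99%, 94% or 74% of trials if SNR is truly equal, but in only about 76%, 43% or 27% if the true ratio is 0.95 (SD 0.2, 0.3, 0.4). Requiring every contrast and tissue to pass lowers the chance further, as Step 3 shows, so the number of comparisons carrying a limit should be chosen deliberately.
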